18.2 Reporting Procedures

It is important to consider the natural history of oesophago-gastric cancer affecting each participant enrolled, the expected sequelae of the illness, and the relevance of these complications to the study treatment. All eligible participants have a poor prognosis, and due to the complexity of their condition are at increased risk of experiencing multiple adverse events. Consequently, only Serious Adverse Events (SAE) will be recorded in this study. This is limited to serious adverse events, which might reasonably occur as a consequence of the study surveillance (i.e. not events that are part of the natural history of the primary disease process or expected complications of oesophagogastric cancer).

SAEs, as defined above (and unless excluding from reporting – see below), experienced by a participant from randomisation until their completion of the study must be reported in the participant's medical notes, on the study CRFs, and reported to the CTU using the SAE Reporting Form, within 24 hours of observing or learning of the SAE(s). The SAE form will be kept on REDCap to enable direct data entry. All sections of the SAE Reporting Form must be completed. The CTU is automatically notified of the SAE report through the database. A paper SAE form should be used as a back-up if the SAE form is not available electronically.

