14 STUDY INTERVENTION AND COMPARATOR

14.1 Intensive surveillance follow-up (intervention)

Participants randomised to the intervention arm will receive intensive surveillance for three years. Participants will have a clinical review with a CT scan of the chest, abdomen and pelvis every 6 months up to 36 months. An endoscopy will also be performed 12 months post-randomisation.

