14.2 Usual care (comparator/control)

Participants randomised to the comparator arm will receive standard care follow-up following their surgery. Standard care comprises of a clinical review at 6 and 12 months and after 12 months, participants are either discharged to primary care or clinically reviewed annually by the treating centre, with targeted investigations as needed. Targeted investigations are recommended in the event of new onset alarm symptoms (see section 14.2.1 below).

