17.2.3 Endoscopy (intervention/active surveillance arm only)

Participants randomised to the intervention arm (intensive surveillance) will have an upper GI endoscopy with or without biopsy at 12 months post-randomisation. Biopsies will be performed if an abnormality is visualised according to each hospital's standard practice, and as per standard of care pathway.

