17.2.5 Further endoscopic/radiological investigation – both arms

Participants randomised to either arm will undergo further endoscopic or radiological investigation for cancer recurrence if they report any of the following symptoms during clinical review either within the study or outside of the study as part of normal clinical practice:

- dysphagia to solid food
- dysphagia to liquids
- vomiting
- abdominal pain
- chest pain
- regurgitation of foods
- unexpected weight loss
- progressive hoarseness of voice.

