20.7 Interim analyses

Given the nature of the primary outcome and the planned study length, no formal comparative interim analyses are planned. However, accumulating data will be reviewed regularly by the Data

Safety and Monitoring Committee (DSMC), including reviewing data by treatment arm and patient safety.

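### Section 18.2 ties SAE recording to an undefined study surveillance that is scheduled in one arm only, so by-arm SAE counts may not be comparable

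*Protocol*

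**What the plan says.** **Recording rule.** Section 18.2 argues that these patients have a poor prognosis and many expected adverse events, so only SAEs are recorded. It then narrows this: "This is limited to serious adverse events, which might reasonably occur as a consequence of the study surveillance". A parenthesis explains that the natural history of the disease and expected complications of the cancer are to be left out. The next paragraph says that SAEs as defined above, unless exempt, "experienced by a participant from randomisation until their completion of the study must be reported"; it names no arm. Section 18.3.1 lists the exemptions.

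**Procedures by arm.** In the intervention arm, section 14.1 says: "Participants will have a clinical review with a CT scan of the chest, abdomen and pelvis every 6 months up to 36 months". It adds: "An endoscopy will also be performed 12 months post-randomisation". The heading of 17.2.3 carries the restriction "Endoscopy (intervention/active surveillance arm only", and 17.2.4 restricts CT in the same way. For controls, section 14.2 says: "Standard care comprises of a clinical review at 6 and 12 months". After that they are discharged or reviewed annually, with targeted investigations as needed. Section 17.2.5 adds for both arms: "Participants randomised to either arm will undergo further endoscopic or radiological investigation for cancer recurrence if they report any of the following symptoms".

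**Use of the data.** Section 20.7 plans no formal comparative interim analysis but has the DSMC review accumulating data, "including reviewing data by treatment arm and patient safety". Under 22.4.2 the DSMC may recommend protocol changes to protect patients. Section 20.8 sets no formal stopping rule.

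**The concern.** An SAE rule phrased as a consequence of an exposure works when both arms have that exposure. Here the most natural referent of study surveillance is a schedule of scans and one endoscopy that belongs to a single arm, while the same procedures are also done in controls as standard care. A perforation after the 12-month study endoscopy is plainly recordable. Whether the same event after a control's symptom-driven endoscopy is recordable depends on how a site reads two undefined words, and site staff know the allocation. Symptom-driven procedures in the intervention arm are equally unclear.

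At stake is the procedural harm of intensive surveillance relative to usual follow-up, which is a difference between arms. With no formal stopping rule, DSMC review by arm is the main safeguard. The results are also meant to inform NICE and other guidelines (28.1, 28.2). The SAP cannot repair this, because it can analyse only what the SAE form collects.

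**Working it through.** The plan states no figure on this point, so there is none to reproduce. The check sets out the possible readings of 18.2 and then what each does to a by-arm count.

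**Readings**

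- **A. Scheduled procedures only.** Study surveillance means the protocol's CT and endoscopy schedule. Symptom-driven procedures fall outside in both arms. The definition of relatedness in 18.3, which refers to research procedures, points this way.
- **B. Everything in the surveillance arm.** Any investigation in the intervention arm counts as part of surveillance; control investigations are standard care and do not.
- **C. Any investigation for recurrence, either arm.** The second paragraph of 18.2 names no arm, and many exemptions in 18.3.1 (housing problems, pre-existing co-morbidities) would be redundant under a narrow scope.

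No passage chooses between them.

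**Illustration, endoscopy only**

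Inputs from the protocol: 476 per arm; 45% three-year mortality in the intervention arm (20.2).

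- Assuming a constant hazard: −ln(0.55)/3 = 0.199 per year; survival at 12 months = exp(−0.199) = 0.82; 476 × 0.819 ≈ 390 scheduled endoscopies.
- Assumed: 30% to 60% of controls have one symptom-driven endoscopy, so c = 476 × 0.30 = 143 to 476 × 0.60 = 286. The upper end borrows the roughly 60% recurrence figure in section 8.
- Assumed: the intervention arm has k × c symptom-driven endoscopies, with k = 0.5, 1 or 1.5.
- Assumed: the same serious-complication risk r for every endoscopy; it cancels from the ratios.

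True excess = r(390 + kc − c). Recorded excess is 390r under A, r(390 + kc) under B, and the true excess under C.

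Ratio of recorded to true excess (c = 143 / c = 286):

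| Reading | k = 0.5 | k = 1 | k = 1.5 |
|---|---|---|---|
| A | 1.22 / 1.58 | 1.00 / 1.00 | 0.85 / 0.73 |
| B | 1.45 / 2.16 | 1.37 / 1.73 | 1.31 / 1.54 |
| C | 1.00 / 1.00 | 1.00 / 1.00 | 1.00 / 1.00 |

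For example, A with k = 1.5 and c = 286 gives 390/(390 + 143) = 0.73. B with k = 0.5 and c = 286 gives (390 + 143)/(390 − 143) = 2.16.

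**Can the protocol fix k?** No. Scheduled tests may replace symptom-driven ones, which lowers k. Against that, the intervention arm has six scheduled reviews and controls have two, after which controls may be discharged (14.2, 17.1), so symptoms have more chances to be reported, which raises k. No rates are given for either arm.

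**Counts.** With r assumed at 0.1% to 0.5%, the recorded excess under A is 390 × 0.001 = 0.39 to 390 × 0.005 = 1.95 events. The largest gap from the truth in the table is under B with c = 286: 286 × 0.005 = 1.43 events. CT and biopsy are not included.

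**The case against.** A reader might infer two stronger things: that control-arm complications are left out altogether, and that the excess harm of surveillance is therefore overstated. The documents support neither.

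On omission, the parenthesis in 18.2 explains the limit as a screen against cancer events, and a perforation or contrast reaction is not one. The protocol usually calls the intervention intensive or active surveillance. The bare word is wider: section 8 speaks of a surveillance period when describing how control-arm investigations are recorded, and section 10.6 uses surveillance for the routine follow-up of non-participants. The next paragraph of 18.2 and the list in 18.3.1 also suggest a broad scope. Outright omission is thus one reading among several.

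On direction, reading A drops symptom-driven events in both arms, so it overstates only if controls have more of them (k below 1) and understates if they have fewer. Only reading B overstates throughout, and nothing in the text requires it.

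It is also fair to say that safety is not among the outcomes in 9.2 and 9.3, that no formal SAE comparison is described, that the likely counts are small, and that investigations with their reasons, deaths and secondary-care use are collected in both arms (14.2.1, 17.2.2).

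All of this limits the claim but does not remove it. Text that supports a broad scope alongside text that supports a narrow one leaves each of about 24 sites to choose. The data collected in both arms are not stated to include complications of investigations with seriousness and causality.

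**Conclusion.** The point holds as a defect of definition and ascertainment. Study surveillance is undefined, its most natural meaning is scheduled in one arm only, and the rest of 18.2 and 18.3.1 point to a wider scope. SAEs from symptom-driven CT, endoscopy or biopsy can go unrecorded or be recorded unevenly by arm and site, so the counts reviewed by the DSMC by arm may not be comparable.

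Direction and size are not determinable from the protocol. The 0.73 to 2.16 range shows only how far the answer depends on the reading and on unknown rates; it rests on the assumed shares, equal risk per procedure and a constant hazard. In events, the effect for endoscopy is probably small. The primary outcome is unaffected. The change should be made because the safety data are otherwise hard to interpret and the remedy is cheap. Sequelae of planned chemotherapy or radiotherapy, which 18.3.1 exempts, are a separate matter.

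**What to change.** Reconcile the two paragraphs of 18.2 with 18.3.1, and define the scope by procedure, not by allocation. For example: in either arm, record an SAE if it might reasonably result from a CT scan, endoscopy, biopsy or other investigation done to look for cancer recurrence, whether scheduled by the protocol or prompted by symptoms. The exclusion of natural-history events can stay.

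Add one field to the SAE form for the trigger (scheduled or symptom-driven). Give these SAEs to the DSMC by arm, with the number of procedures as denominator. Further investigations are already on the CRF in both arms, so the denominators need little new collection.

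The cost is one sentence in an amendment, one form field and a few more SAE reports. Only recording changes: no procedure is added, and who is investigated, and when, stays as it is.

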18.3 Review of SAEs by the Sponsor/CTU Nominated Person

An appropriately qualified person will review the SAE and raise any queries with the reporting site. If the site has not provided an assessment of causality and has not responded to the query, it will be assumed that the event reported is related to the study procedures/intervention. The site will be encouraged to respond and if a response is not provided the CI will be consulted by the CTU and the CTU will complete the Sponsor part of the SAE report.

A SAE occurring to a participant will be reported to the Research Ethics Committee (REC) that gave a favourable opinion of the study where in the opinion of the Chief Investigator the event was 'related' (resulted from administration of any of the research procedures) and 'unexpected' in relation to those procedures. Reports of related and unexpected SAEs should be submitted within 15 working days of the Chief Investigator becoming aware of the event, using the Health Research Authority (HRA) report of serious adverse event form.

18.3.1 Events exempt from being reported as SAEs

The following hospitalisations are not considered a SAE:

- a visit to the emergency room or other hospital department < 24 hours, that does not result in admission (unless considered an important medical or life-threatening event)
- o admissions as per protocol for a planned medical/surgical procedure
- o admissions for planned chemotherapy and/or radiotherapy and any related sequelae
- routine health assessment requiring admission for baseline/trending of health status (e.g. routine colonoscopy)
- medical/surgical admission other than to remedy ill health and planned prior to entry into the study
- admission encountered for another life circumstance that carries no bearing on health status and requires no medical/surgical intervention (e.g., lack of housing, economic inadequacy, caregiver respite, family circumstances, administrative reason)
- admission for administration of anticancer therapy in the absence of any other SAEs (applies to oncology protocols)
- non-surgical sequelae which can result from any operative procedure or a diagnosis of malignancy (for example, but not limited to: pneumonia, urinary tract infection, pulmonary embolism, deep vein thrombosis)
- o unplanned admissions resulting from pre-existing co-morbidities recorded at baseline

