18.1.3 Serious Adverse Event (SAE)

A serious adverse event is any untoward medical occurrence that:

- results in death
- is life-threatening
- requires inpatient hospitalisation or prolongation of existing hospitalisation
- results in persistent or significant disability/incapacity
- may have caused a congenital anomaly/birth defect

Other 'important medical events' may also be considered a serious adverse event when, based upon appropriate medical judgment, the event may jeopardise the participant and may require medical or surgical intervention to prevent one of the outcomes listed above.

Note: The term "life-threatening" in the definition of "serious" refers to an event in which the participant was at risk of death at the time of the event; it does not refer to an event which hypothetically might have caused death if it were more severe.

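### The SAE exemptions in section 18.3.1 have no exception for suspected relatedness, so a non-fatal admission such as pneumonia after the study endoscopy can go unreported

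*Protocol*

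**What the plan says.** Section 18.1.3 defines an SAE in the usual way. One criterion is an event that "requires inpatient hospitalisation or prolongation of existing hospitalisation"; death, threat to life, lasting disability and other important medical events are separate criteria.

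Section 18.2 records SAEs only, on the ground that these patients will have many adverse events from their disease, and narrows the scope further: "This is limited to serious adverse events, which might reasonably occur as a consequence of the study surveillance". The next paragraph sets the reporting duty with a condition attached: "SAEs, as defined above (and unless excluding from reporting – see below".

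The exemptions are in section 18.3.1, which opens "The following hospitalisations are not considered a SAE". Two items matter here:

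- "non-surgical sequelae which can result from any operative procedure or a diagnosis of malignancy", with the illustration "for example, but not limited to: pneumonia, urinary tract infection, pulmonary embolism, deep vein thrombosis";
- "unplanned admissions resulting from pre-existing co-morbidities recorded at baseline".

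The only override in the list is "unless considered an important medical or life-threatening event". It belongs to the item on short emergency-department visits.

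**The concern.** The two sections point in different directions. Section 18.2 sets aside almost everything except possible harm from surveillance, so detecting that harm is the purpose of SAE capture in this trial. Section 18.3.1 then removes a class of admissions by type of event, and 18.2 says that the list prevails. An event suspected to come from a study procedure can therefore fall outside reporting because of its diagnosis.

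The scheduled study CT scans and endoscopy take place only in the intervention arm (sections 17.1, 17.2.3 and 17.2.4). A gap in reporting their complications falls on the harms of the strategy under test. The DSMC reviews the safety data that the trial generates (section 22.4.2), so it cannot weigh an event for which no form was completed. Sites may also differ: one may report a post-endoscopy pneumonia as surveillance-related while another exempts it because pneumonia is on the list.

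**Working it through.** No sample size, error rate or event count is involved, so the check sets the clauses side by side and follows one case through them.

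**Case:** a participant in the intervention arm is admitted with pneumonia after the 12-month study endoscopy, survives, and is not in immediate danger of death.

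1. *Is it an SAE under 18.1.3?* Yes, on the hospitalisation criterion.
2. *Is it within the scope that 18.2 sets?* Yes. It might reasonably follow from a study procedure.
3. *Is the duty to report unconditional?* No. "SAEs, as defined above (and unless excluding from reporting – see below" makes it subject to 18.3.1.
4. *Does 18.3.1 exempt it?* Read literally, yes. It is a hospitalisation, pneumonia is named, and the item asks what such an event can result from, not what caused this one. The examples are expressly not exhaustive.
5. *Does the list make an exception for suspected relatedness?* No. The single override concerns seriousness and is tied to emergency-department visits.

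**Does another section restore the duty?**

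| Section | What it does | Effect on the case |
|---|---|---|
| 18.3 | Treats an SAE as related if the site gives no causality assessment | Applies only once an event has been reported |
| 18.4 | Requires a causality statement for deaths | Does not reach non-fatal admissions |
| 18.5 | Adds further exclusions for planned admissions | None |
| 18.2 | Records SAEs only | No non-serious adverse-event record to fall back on |
| 17.2.2 | Collects secondary-care resource use every 6 months | The admission may be counted, but no causality assessment is listed |

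None of them does. Section 18.4 asks whether a causal link to the intervention is suspected. The protocol therefore applies a relatedness test to deaths but has none for the exempt hospitalisations.

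**Scale.** With 476 participants in the intervention arm and one endoscopy each, there are at most 476 × 1 = 476 scheduled study endoscopies, before death, withdrawal or non-attendance. This counts opportunities, not missed events. The protocol gives no complication rate, so it cannot be turned into a number of unreported SAEs.

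**The case against.** The strongest defence is that 18.3.1 illustrates 18.2. Every participant has recently had a cancer resection, so the item on non-surgical sequelae is naturally taken to screen out post-operative and cancer-related events, which 18.2 already sets aside. On that view pneumonia is an example of a sequela of surgery or cancer, and pneumonia caused by an endoscopy was never meant. This is a fair account of the probable intention. However, the wording refers to any operative procedure and to what an event can result from, so it permits the literal reading, and the condition in 18.2 gives the list priority.

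A reader might infer more: that the list overrides the reporting of surveillance harms in general. The documents do not support that, for these reasons.

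- The list concerns hospitalisations. Deaths and life-threatening events can still be SAEs on other criteria, and deaths have their own causality statement in 18.4.
- Perforation, bleeding and contrast reactions are not named and, on a plain reading, stay reportable.
- The co-morbidity item already turns on cause: it exempts admissions "unplanned admissions resulting from pre-existing co-morbidities recorded at baseline". An admission caused by a study scan results from the scan. A co-morbidity made worse by a scan is arguable, not plainly exempt.
- The CT case therefore rests on that item or on the open-ended wording of the sequelae item, and is weaker than the endoscopy case.
- The REC receives individual SAEs that are both related and unexpected (section 18.3), not a rate. A recognised complication that counts as expected would not go to it even without the exemption.

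The DSMC also reviews accumulating data by arm (section 20.7). That softens the consequence, but it does not supply a causality assessment for an admission that was never reported.

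**Conclusion.** The point holds in a limited form. As written, 18.2 yields to 18.3.1, and the item on non-surgical sequelae exempts a named diagnosis with no exception for suspected relatedness. A site that follows the text can leave a non-fatal, non-life-threatening admission, such as pneumonia after the study endoscopy, off the SAE record although it is what 18.2 sets out to capture.

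The consequence is a possibly incomplete record of intervention-arm harms before the DSMC, and inconsistent reporting between sites. The size cannot be given, because the protocol states neither a complication rate nor how often a complication would take an exempt form. The conclusion rests on reading the sequelae item literally. If the authors meant only sequelae of the cancer resection, the fault is one of wording, and the same sentence cures it. The primary outcome and its analysis are not affected.

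**What to change.** Reconcile 18.2 and 18.3.1 by adding to 18.3.1:

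> None of these exemptions applies where the event is suspected to be related to a study procedure (CT scan, endoscopy or biopsy); such events are reported under 18.2.

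The sentence keeps the list's purpose of filtering out events due to the cancer, its surgery or planned care. It also settles the weaker CT and co-morbidity cases without a debate over their wording. It concerns reporting only and changes nothing in patient care. The cost is one sentence in a protocol amendment, a note to sites, and a few more SAE forms.

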18.4 Death during the study

Death due to disease under study is to be recorded on the Death CRF form providing the death is not unexpected or if a causal relationship with the study intervention is suspected. The investigator must clearly state whether the death was expected or unexpected and whether a causal relationship to the study intervention is suspected.

